## COVID-19 Statistical Analysis Plan

DAIDS Term	Laboratory Test	No Event	Grade 1	Grade 2	Grade 3	Grade 4
Sodium, High	Sodium (mmol/L)	< 146	146 to < 150	150 to < 154	154 to < 160	≥ 160
Sodium, Low	Sodium (mmol/L)	≥ 135	130 to < 135	125 to < 130	121 to < 125	≤ 120
Potassium, High	Potassium (mmol/L)	< 5.6	5.6 to < 6.0	6.0 to < 6.5	6.5 to < 7.0	≥ 7.0
Potassium, Low	Potassium (mmol/L)	≥ 3.4	3.0 to < 3.4	2.5 to < 3.0	2.0 to < 2.5	< 2.0
Bicarbonate, Low	Bicarbonate (mmol/L)	≥ LLN	16.0 to < LLN	11.0 to < 16.0	8.0 to < 11.0	< 8.0
Calcium, High	Calcium (mmol/L)	< 2.65	2.65 to < 2.88	2.88 to < 3.13	3.13 to < 3.38	≥ 3.38
Calcium, Low	Calcium (mmol/L)	≥ 2.10	1.95 to < 2.10	1.75 to < 1.95	1.53 to < 1.75	< 1.53
Magnesium, Low	Magnesium (mmol/L)	≥ 0.70	0.60 to < 0.70	0.45 to < 0.60	0.30 to < 0.45	< 0.30

\*Will be determined from subject's Adverse Events page and identified by the medical team.

#### Hematology Tests:

Document: \\[REDACTED]net\enterprise\Apps\sasdata\SASb\SAS\Atea\_Pharmaceuticals\AT-527\SZA63631\Biostatistics\Documentation\SAP\AT-03A-001\_SAP\_V1.0\_COVID\_SAP\_PA7.doc

Author: [REDACTED]

Version Number: V1.0

Version Date: 15Apr2021

Template No.: CS\_TP\_BS016 Revision 6

Effective Date: 02Dec2019

Reference: CS\_WI\_BS005

Copyright © 2009, 2010, 2012, 2016, 2018, 2019 [REDACTED] All rights reserved. The contents of this document are confidential and proprietary to [REDACTED] Holdings Inc. and its subsidiaries. Unauthorized use, disclosure or reproduction is strictly prohibited.

## COVID-19 Statistical Analysis Plan

DAIDS Term	Laboratory Test	No Event	Grade 1	Grade 2	Grade 3	Grade 4
Hemoglobin, Low	Hemoglobin (g/L)	Male: $\geq 109$ ; Female: $\geq 104$	Male: 100 to 109; Female: 95 to 104	Male: 90 to < 100; Female: 85 to < 95	Male: 70 to < 90; Female: 65 to < 85	Male: < 70; Female: < 65
WBC, Decreased	White blood cell count total (x10E9/L)	> 2.499	2.000 to 2.499	1.500 to 1.999	1.000 to 1.499	< 1.000
Absolute Neutrophil Count, Low	Absolute neutrophils count (x10E9/L)	> 1.000	0.800 to 1.000	0.600 to 0.799	0.400 to 0.599	< 0.400
Absolute Lymphocyte Count, Low	Absolute lymphocyte count (x10E9/L)	$\geq 0.650$	0.600 to < 0.650	0.500 to < 0.600	0.350 to < 0.500	< 0.350
Platelets, Decreased	Platelet count (x10E9/L)	$\geq 125.000$	100.000 to < 125.000	50.000 to < 100.000	25.000 to < 50.000	< 25.000

## Coagulation Tests:

Document: \\[REDACTED]net\enterprise\apps\sasdata\SASb\SAS\Atea\_Pharmaceuticals\AT-527\SZA63631\Biostatistics\Documentation\SAP\AT-03A-001\_SAP\_V1.0\_COVID\_SAP\_PA7.doc

Author: [REDACTED]

Version Number: V1.0

Version Date: 15Apr2021

Template No.: CS\_TP\_BS016 Revision 6

Effective Date: 02Dec2019

Reference: CS\_WI\_BS005

Copyright © 2009, 2010, 2012, 2016, 2018, 2019 [REDACTED] All rights reserved. The contents of this document are confidential and proprietary to [REDACTED] Holdings Inc. and its subsidiaries. Unauthorized use, disclosure or reproduction is strictly prohibited.

COVID-19 Statistical Analysis Plan

DAIDS Term	Laboratory Test	No Event	Grade 1	Grade 2	Grade 3	Grade 4
PT, High	Prothrombin time (s)	< 1.1 x ULN	1.1 to < 1.25 x ULN	1.25 to < 1.50 x ULN	1.50 to < 3.00 x ULN	≥ 3.00 x ULN
INR, High	International normalized ratio	< 1.1 x ULN	1.1 to < 1.5 x ULN	1.5 to < 2.0 x ULN	2.0 to < 3.0 x ULN	≥ 3.0 x ULN

Urinalysis Tests:

DAIDS Term	Laboratory Test	No Event	Grade 1	Grade 2	Grade 3	Grade 4
Glycosuria	Glucose	Criteria for Grade 1-3 not met	Trace to 1+ or $\leq 250$ mg	2+ or $> 250$ to $\leq 500$ mg	$> 2+$ or $> 500$ mg	NA
Proteinuria	Protein	Criteria for Grade 1-3 not met	1+	2+	3+ or higher	NA

Document: \\[REDACTED]net\enterprise\Apps\sasdata\SASb\SAS\Atea\_Pharmaceuticals\AT-527\SZA63631\Biostatistics\Documentation\SAP\AT-03A-001\_SAP\_V1.0\_COVID\_SAP\_PA7.doc

Author: [REDACTED]

Version Number: V1.0

Version Date: 15Apr2021

Template No.: CS\_TP\_BS016 Revision 6

Effective Date: 02Dec2019

Reference: CS\_WI\_BS005

Copyright © 2009, 2010, 2012, 2016, 2018, 2019 [REDACTED] All rights reserved. The contents of this document are confidential and proprietary to [REDACTED] Holdings Inc. and its subsidiaries. Unauthorized use, disclosure or reproduction is strictly prohibited.

## APPENDIX 5. NATIONAL EARLY WARNING SCORE (NEWS)

Physiological parameters	3	2	1	0	1	2	3
Respiration Rate (breaths per minute)	$\leq 8$		9–11	12–20		21–24	$\geq 25$
$S_pO_2$ (%)	$\leq 91$	92–93	94–95	$\geq 96$			
Any supplemental oxygen?		Yes		No			
Temperature (°C)	$\leq 35.0$		35.1–36.0	36.1–38.0	38.1–39.0	$\geq 39.1$	
Systolic BP (mmHg)	$\leq 90$	91–100	101–110	111–219			$\geq 220$
Heart/pulse rate (beats per minute)	$\leq 40$		41–50	51–90	91–110	111–130	$\geq 131$
Level of consciousness using the AVPU system				A			V, P or U

Level of consciousness: A=alert; V=responds to voice; P=responds to pain; U=unresponsive. Modified from National Early Warning Score (NEWS): Standardising the assessment of acute-illness severity in the NHS. Report of a working party. Royal College of Physicians, London, 2012.

Document: \\[REDACTED]\net\enterprise\Apps\sasdata\SASb\SAS\Atea\_Pharmaceuticals\AT-527\SZA63631\Biostatistics\Documentation\SAP\AT-03A-001\_SAP\_V1.0\_COVID\_SAP\_PA7.doc

Author: [REDACTED]

Version Number: V1.0

Version Date: 15Apr2021

Template No.: CS\_TP\_BS016 Revision 6

Effective Date: 02Dec2019

Reference: CS\_WI\_BS005

Copyright © 2009, 2010, 2012, 2016, 2018, 2019 [REDACTED] All rights reserved. The contents of this document are confidential and proprietary to [REDACTED] Holdings Inc. and its subsidiaries. Unauthorized use, disclosure or reproduction is strictly prohibited.

Changes to Planned Statistical Analyses Form

Page 1 of 3

Customer: ATEA Pharmaceuticals  
Protocol No.: AT-03A-001  
Project Code: SZA63631  
Date (DDMMYYYY): 16Mar2022

The timing of the change(s) was:

- After unblinding (or database lock for an open-label study) but before completion of the final Statistical Report/Clinical Study Report
- After completion of the final Statistical Report/Clinical Study Report

Describe the change(s) required:

- Precision on how to handle the subjects having a treatment start date the day after the date of randomization and who have a recovery ON Day 14. They will have time to recovery of 15 days and we will set those without recovery to 15.01 days. (Tables 14.2.3.X)
- Using 65 for age group instead of 70. (Table 14.1.4.1, 14.2.1.3, 14.2.2.3, 14.2.3.3, 14.2.4.3)
- Hypertension co morbidities will use MHTERM=Hypertension instead of baseline diastolic and systolic values. (Tables 14.1.4.1 and 14.1.4.2)
- Updated derivation for symptom resolution: Time to symptom resolution (days) = (Latest post-baseline assessment symptom end date – Date of randomization) +1. (Tables 14.2.4.X)
- We clarified in footnote that we are using both TaqPath and COBAS tests results for mITT population. (See footnotes in tables)
- For titer data we updated AVAL to 1.2 and 0.45 respectively for results <1.5 and <0.75 in summaries:
  - o It is as per Atea's virologist request and the logic is (Tables 14.2.5.5 and 14.2.4.6):
    - For "<1.5", we should use 15.8, i.e.  $[10^{1.5}]/2$ , as the untransformed value which is 1.2 on log10 scale.
    - For "<0.75", we'll use 2.8, i.e  $[10^{0.75}]/2$ , as the untransformed value which is 0.45 on the log10 scale.
- Time to Sustained Non-detectable SARS-CoV-2 will be displayed by method (COBAS/ TaqPath). (Table 14.2.5.4)
- Level of SARS-CoV-2 Infectious Titer analysis will use the same approach as for the "Time to sustained non-detectable SARS-CoV-2 (mITT)" output, we will be providing estimates of proportion of subjects with undetectable/negative results, using K-M estimates. (Table 14.2.5.6)
- For all tests except ANCOVA, the 2-sided pvalue will be displayed.
- Childbearing potential and HgbA1c are not included in Demographics and baseline characteristics table. (Tables 14.1.4.1 and 14.1.4.2)
- ANCOVA analysis: Present the Change-from-Baseline LSM (SE) for each treatment group. (Table 14.2.5.1)
- Subject level deviations and site level deviations are listed separately.
- Information present in the SAP which are not presented:
  - o Subjects with screen failure.
  - o Inclusion and exclusion summary.
  - o Deviation summary.
  - o Medical History summary.
  - o Disease history summary.
  - o Medication summary.
  - o Exposure summary.

Form No: CS\_FM\_BS006 Revision 8  
Effective Date: 15Jan2020

Reference: CS\_WI\_BS005, CS\_WI\_BS013

## Changes to Planned Statistical Analyses Form

Page 2 of 3

Customer:	ATEA Pharmaceuticals
Protocol No.:	AT-03A-001
Project Code:	SZA63631
Date (DDMMYYYY):	16Mar2022

- PRI sensitivity analysis (except on mITT analysis set).
- PRI supplementary analysis (except on subgroups).
- Proportion of subjects with respiratory failure or death (RFD) by Day 28.
- Sensitivity analyses for key secondary efficacy endpoints.
- Proportion of subjects improving/worsening from baseline in clinical status.
- All-cause mortality.
- Duration of hospitalization.
- Time to first SARS-CoV-2 Negative Test.
- Proportion of subjects SARS-CoV-2 positive at each time point.
- Sensitivity analysis for time to clinical recovery by day 14.
- All other secondary efficacy analysis.
- All exploratory analysis except level of SARS-CoV-2 infection virus titer over time and time-weighted average change from baseline in quantitative SARS-CoV-2.
- Treatment emergent adverse events by relationship to study treatment summary.
- Treatment emergent adverse events by relationship to non-study treatment summary.
- Treatment emergent adverse events leading to discontinuation from study summary.
- Death summary.
- Laboratory evaluations summary.
- Vital signs summary.
- ECG summary.
- Physical examination summary.

- The study is conducted in 2 Parts. Part A evaluates an AT-527 dose of 550 mg BID for 5 days and Part B evaluates a dose of 1100 mg BID for 5 days. Part B patients will only be listed.

Describe the process used to decide on the change(s) and who was involved:

While creating the shells and working on the Interim Analysis (IA) outputs it appeared some updates were needed. As the study is terminating early, the IA tables/figures outputs will be used for the final delivery. Atea and [REDACTED] biostatistical teams were involved.

The group(s) responsible for the change(s) and implications for the study:

[REDACTED] Biostatistical team will deliver the datasets and outputs according to these updates. The SAP will not be updated.

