- In Part A, a cohort of 20 subjects was initially enrolled to preliminarily assess the safety of the 550 mg BID dosing regimen. Enrollment was paused after the first 20 subjects, until the DSMB conducted a safety review. Upon DSMB review, a second cohort of 20 subjects was enrolled in Part A and enrollment was paused until the DSMB conducted a safety review of these data. Again, the DSMB allowed the study to continue without modification.
- In order to perform the interim analysis, Part A enrollment was paused by the Sponsor after 81 subjects were randomized. As described in [Section 1.1](#), no additional subjects will be randomized in Part A with implementation of Amendment 8.
- Part B subjects will be randomized (1:1) to one of the two following arms:

Disease Severity	Treatment Duration	Dosing Arms	
Moderate	5 days	active	1100 mg AT-527 administered every ~12 hours (10 doses) + SOC
		placebo	AT-527 placebo administered every ~12 hours (10 doses) + SOC

*Randomized 1:1 (active:placebo)

- Up to an additional 110 subjects will be enrolled in Part B.
- An additional DSMB safety review will occur when 50% of the Part B subjects have been enrolled.

For each interim safety review, pooled safety data will be reviewed by the DSMB. The DSMB will alert the Sponsor if there are any safety concerns for active-treated subjects compared to placebo recipients.

Protocol Number: AT-03A-001

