5.4.2. Administration Instructions

Part A

Subjects will take one (1) tablet (550 mg AT-527 or placebo x 1) administered approximately every 12 hours (i.e. BID) for the 5-day treatment period.

Part B

Subjects will take two (2) tablets (550 mg AT-527 or placebo x 2) administered approximately every 12 hours (i.e. BID) for the 5-day treatment period.

Study drugs will be taken orally and should be taken at approximately the same time each day, ideally within an approximate 2 hour window (as a guidance). The drugs may be given with water. Previous studies indicate no appreciable effect of food on AT-527 absorption, so study dosing can be done between or during mealtimes. Regular daily timing is preferred, to consistently achieve dose intervals of approximately 12 hours. Dosing on Day 1 can occur at any time of day (AM or PM).

If a dose is missed, subjects should be instructed to take the missed dose(s) of study drugs as soon as possible during the same day. Subjects should never double the next dose with a missed dose.

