8.2. Endpoints

8.2.1. Primary Efficacy Endpoint and Sample Size Calculations

Part A

The primary endpoint for Part A of this study is the proportion of subjects with PRI, defined as a ≥ 2 -tier increase in respiratory support methods required to maintain satisfactory oxygenation ($\text{SpO}_2 \geq 93\%$), using the 6-tier hierarchical scale of Respiratory Support methods described in **Section 6.9**.

The primary efficacy goal is to reduce the incidence of PRI by 50% for active-dosed subjects compared to placebo recipients. The featured timeframe for this primary endpoint analysis will be the 14-day primary study period, with secondary analyses at study Days 10, 21, and 28.

With this study's relatively high-risk COVID-19 subject population (one or more known risk factors for poor outcomes), the study postulate is that 40% of placebo recipients will experience PRI during the 14-day study period, and the efficacy goal is therefore to reduce that incidence of PRI to 20% or less in active recipients.

Assuming PRI rates (PRIR) of 0.4 and 0.2 in the control and experimental arms, respectively, at alpha one-sided of 0.025, and at a power of 0.8, a total of 182 subjects are required at a 1:1 allocation, i.e. 91 per study arm. The study statistical hypotheses are as follows:

$$H_0: \text{Experimental}_{\text{PRIR}} \geq \text{Control}_{\text{PRIR}}$$

$$H_a: \text{Experimental}_{\text{PRIR}} < \text{Control}_{\text{PRIR}}$$

Part B

The primary endpoint of Part B is the change from baseline in amount of SARS-CoV-2 virus RNA (viral load) as measured by RT-PCR. Viral load will be assessed quantitatively using a validated assay. Analyses will be carried out at each scheduled time point using the mITT population. Part B of the study is signal seeking. The primary analysis aims to identify and characterize any potential effect of AT-527 on viral load over time. Analyses and p-values are descriptive and no adjustment for multiple comparisons will be made.

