## 3. STUDY DESIGN

### 3.1. GENERAL DESCRIPTION

This is a phase 2 double-blind, placebo-controlled, randomized treatment study evaluating AT-527 (or placebo) for 5 days in combination with supportive standard of care (SoC) compared to SoC alone in hospitalized/confined subjects with moderate COVID-19 disease and risk factors for poor outcomes. The study will enroll adults, age  $\geq 18$  years of age, with moderate COVID-19, not on a ventilator. Subjects must also have at least one of the known common risk factors for poor outcomes: obesity (BMI $>30$ ), hypertension, diabetes or asthma. Subjects will be documented as SARS-CoV-2 positive in an assay granted Emergency Use Authorization (EUA) by the U.S. Food and Drug Administration (FDA).

Moderate disease will be defined by the following:

- Symptoms of lower respiratory infection with COVID-19, with initial symptom onset within 5 days prior to Screening:
  - At least 1 of the following: fever ( $> 38.3^{\circ}\text{C}$ ), cough, sore throat, fatigue/malaise, headache, muscle pain, or more significant lower respiratory symptoms including dyspnea (at rest or with exertion)
- Clinical signs indicative of lower respiratory infection with COVID-19 (as above), with:
  - $\text{SpO}_2 \geq 93\%$  on room air or requires  $\leq 2\text{L}/\text{min}$  oxygen by nasal cannula or mask to maintain  $\text{SpO}_2 \geq$

Document: \[REDACTED]\net\enterprise\Apps\sasdata\SASb\SAS\Atea\_Pharmaceuticals\AT-527\527\527A63631\Biostatistics\Documentation\SAP\AT-03A-001\_V1.0\_COVID\_SAP\_PA7.doc

Author: \[REDACTED] Version Number: V1.0  
Version Date: 15Apr2021

Template No.: CS\_TP\_BS016 Revision 6

Reference: CS\_WI\_BS005

Effective Date: 02Dec2019

Copyright © 2009, 2010, 2012, 2016, 2018, 2019 \[REDACTED] All rights reserved. The contents of this document are confidential and proprietary to \[REDACTED] Holdings Inc. and its subsidiaries. Unauthorized use, disclosure or reproduction is strictly prohibited.

COVID-19 Statistical Analysis Plan

ATEA Pharmaceuticals  
Protocol AT-03A-001  
Page 12 of 77

93%

Subjects will be randomized 1:1 (active:placebo). Subjects will receive one (1) tablet of 550 mg active drug (or matching placebo) every ~12 hours to complete **5 days** of treatment.

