### 15.1. DERIVATIONS

Proportion of planned dose received will be calculated as follows:

- Proportion = Number of tablets taken / Number of planned tablets

Document: \[REDACTED]\net\enterprise\Apps\sasdata\SASb\SAS\Atea\_Pharmaceuticals\AT-527\SAZ\A63631\Biostatistics\Documentation\SAP\AT-03A-001\_V1.0\_COVID\_SAP\_PA7.doc  
Author: \[REDACTED]

Version Number: V1.0  
Version Date: 15Apr2021

Template No.: CS\_TP\_BS016 Revision 6

Reference: CS\_WI\_BS005

Effective Date: 02Dec2019

Copyright © 2009, 2010, 2012, 2016, 2018, 2019 \[REDACTED] All rights reserved. The contents of this document are confidential and proprietary to \[REDACTED] Holdings Inc. and its subsidiaries. Unauthorized use, disclosure or reproduction is strictly prohibited.

where:

- Number of tablets taken = (total number of tablets dispensed – total number of tablets returned)
- Number of planned tablets = 10

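### The final change form limits the randomised Part B to listings, so no by-arm result is reported for its primary endpoint or for safety at 1100 mg BID

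*SAP*

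**What the plan says.** The protocol sets Part B up as a randomised comparison. Section 3.1 states: "Part B subjects will be randomized (1:1) to one of the two following arms", namely 1100 mg BID or placebo, in up to 110 subjects. Section 8.2.1 states: "The primary endpoint of Part B is the change from baseline in amount of SARS-CoV-2 virus RNA (viral load) as measured by RT-PCR". Section 8.3.1 compares the arms by ANCOVA in the mITT set, adjusting for log10 baseline viral load, and reports least squares means, their difference, 95% CIs and p-values. Sections 8.2.5 and 8.4 compare safety between the two treatments and summarise it by treatment group. The synopsis has efficacy analysed separately for Parts A and B unless otherwise indicated. Section 8.2.1 also calls Part B signal seeking, with descriptive p-values and no multiplicity adjustment.

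SAP V1.0 (15 April 2021) covers the 550 mg design only. Its Section 3.1 says "Subjects will receive one (1) tablet of 550 mg active drug (or matching placebo", and it contains no Part B analysis.

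The change form of 16 March 2022 then says "Part B patients will only be listed". Its explanation of the changes as a whole includes "As the study is terminating early, the IA tables/figures outputs will be used for the final delivery", and it closes the matter with "The SAP will not be updated".

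**The concern.** According to Sections 1.1 and 1.2.2 of the protocol, Part B was added to learn whether the higher dose has a more pronounced antiviral effect, to describe the dose-exposure-response relation and to support dose selection. It is this trial's only randomised evidence at that dose. A listing shows each subject's values but gives no arm mean, no difference from placebo, no interval and no event rate. If the form is followed, a reader of the trial report sees a stated primary endpoint with no result and a doubled dose with no adverse event frequency beside its concurrent placebo.

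The form explains the change by early termination and by issues found while preparing the interim outputs. Neither is specific to Part B, and no count or minimum size is given that would show why a table is not worthwhile.

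**Working it through.** **1. Do the reused outputs cover Part B?** Protocol Section 1.1 and SAP Section 4.2 describe the interim analysis as covering the first 70 randomised subjects. Part A alone randomised 81 (protocol Section 3.1), and Part B was added afterwards by Amendment 8. The interim therefore held no Part B subject. Even if the same tables were re-run on all of Part A, the form still confines Part B to listings.

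**2. Does any other text restore a Part B summary?** None does in the documents as supplied. SAP V1.0 has no Part B content, and the form says it stays as it is.

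**3. The plan's own Part B figure.** Protocol Section 8.2.1 assumes a difference of 0.7 log10, SD 1.8, 100 analysable patients (50 per arm) and a one-sided 0.1 level, and states at least 90% power.

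- SE = 1.8 × √(2/50) = 0.36
- 0.7/0.36 = 1.944, and 1.944 − 1.282 = 0.663
- Power = Φ(0.663) = 74.6% (74.4% with the t distribution)

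The stated 90% does not reproduce from these inputs. That is a separate matter, and the present point does not depend on it.

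**4. What a by-arm estimate would look like.** Part B enrolment is not given, so the sizes below are assumptions. SE = 1.8 × √(2/n), and the 95% half-width is t(0.975, 2n − 2) × SE.

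| Assumed n per arm | SE (log10) | 95% CI half-width (log10) |
|---|---|---|
| 5 | 1.14 | 2.63 |
| 10 | 0.80 | 1.69 |
| 20 | 0.57 | 1.15 |
| 30 | 0.46 | 0.93 |
| 50 (planned) | 0.36 | 0.71 |

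These use the unadjusted SD. Baseline adjustment would narrow the intervals by an amount the documents do not allow one to calculate. Against a planning effect of 0.7, small numbers give a very imprecise estimate.

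**5. A consequence for any Part B exposure table.** SAP Section 15.1 fixes "Number of planned tablets = 10". For Part B, protocol Section 5.4.2 says "Subjects will take two (2) tablets (550 mg AT-527 or placebo x 2", twice daily for 5 days, so the planned count is 2 × 2 × 5 = 20. Using 10 would show full adherence as 20/10 = 200%.

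**The case against.** The strongest reply is that listings are proportionate for a truncated cohort. The form's authors probably knew how many Part B subjects there were. If there were only a handful, an ANCOVA would say almost nothing. This stands in part: the severity of the point depends on a number the documents withhold. It does not remove the need to state that number, and descriptive by-arm values need no minimum size.

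Other readings go further than the documents allow:

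- **The Part B data are lost or cannot be pooled.** SAP Appendix 2 orders listings by treatment group, and the form promises datasets as well as outputs. By-arm rates and pooling remain possible from subject-level data. Only the reported summaries are missing.
- **A confirmatory result is lost.** Part B was signal seeking, protocol Section 8.2.2 requires any finding to be confirmed in another study, and SAP Section 17 plans no statistical comparison of safety.
- **The arms were never compared for safety.** Protocol Section 10.1 provides a DSMB review at 50% of Part B enrolment, with authority to unblind. Whether that point was reached is not stated, and a DSMB review is in any case not a reported result.
- **The outputs will show 200% compliance, or mix 550 mg and 1100 mg in one AT-527 column.** As the form stands neither will happen in a table, because Part B is not summarised and the exposure summary is dropped. Both matter only once Part B tables are made.
- **Part B was dropped because of its results.** Both timing options legible on the form fall after unblinding or later, but which one applied is not visible, and nothing links the decision to the data.

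**Conclusion.** The point holds as a reporting gap. Under the form, the trial presents no by-arm result for the Part B primary endpoint and no by-arm safety summary for 1100 mg BID. Both were planned, and no reason specific to Part B is recorded.

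The loss is confined to the planned estimates and summaries. Its practical weight cannot be fixed from the documents: the CI half-width for the viral-load difference would run from about 0.7 log10 at the planned 50 per arm to about 1.7 at an assumed 10 per arm and 2.6 at an assumed 5. These figures rest on the protocol's SD of 1.8, equal arms and no gain from baseline adjustment. No minimum arm size for the model can be derived from the documents.

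**What to change.** Replace the listing-only sentence with a statement that Part B is summarised by randomised arm, with 1100 mg and its concurrent placebo in their own columns, separate from Part A. Report:

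- the number randomised and the number evaluable in each arm;
- observed log10 viral load and change from baseline, by visit and arm;
- by-arm counts of TEAEs, SAEs and deaths;
- the ANCOVA difference of protocol Section 8.3.1 with its 95% CI, labelled descriptive, where the numbers allow the model to be fitted. Otherwise, state the Part B numbers and that they are why no model is run.

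If an exposure summary is produced for Part B, use 20 planned tablets.

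The cost is modest. The form keeps an ANCOVA table (14.2.5.1), and the protocol's Part B model has the same terms as the Part A model. The overall TEAE and SAE summaries are not on the form's list of dropped outputs. The separate death summary is on that list, so death counts may need a little new programming. The other downside is wide intervals if few subjects were enrolled, which the reported numbers would make plain.
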